### 8.1 Clinical Study Protocol C-SY 00093

A multicenter clinical study was conducted at four sites in Israel in 2017. Sixty-Six subjects were enrolled (40 Men (61%) and 26 Women (39%), BMI <40), of which three failed to ingest the capsule, including one subject with a known swallowing disorder which was not disclosed to the study team during screening. Forty-Three had polyp(s) (65%) as indicated by their prior recent colonoscopy reports and the other 23 were considered as average risk population without any prior information about their colon.

All study procedures were completed and feedback from most subjects was positive and reassuring that the procedure was well-tolerated.

All capsules (except one) were collected and retrieved for QA inspection. They were all found to be intact and hermetically sealed.

The total transit time (TTT) is measured in hours between capsule ingestion to excretion. The TTT is the sum of 3 distinct sections:

- Time until reaching the caecum
- Time capsule dwells in the caecum
- Time of colon passage until excretion

The following table is the summary of all 63 cases in whom the study was completed (3 did not ingest). The standard deviation (STD) is quite high due to the considerable variability in bowel motility.

	Total Transit Time	Time to Caecum	Time in Caecum	Passage in colon
Average (hours)	52.3	15.9	16.8	16.5
STD	32.9	13.7	18.8	12.1

Table 2: Average transit time of the 3 sections of the GI tract and the standard deviation in each one.

There were no cases of C-Scan capsule retention (medical definition of Capsule retention is when TTT is longer than 300 hours – about 13 days).

The C-Scan is designed to operate continuously for 100 hours. There was one case in which the capsule was retained for 100-200 hours and then removed during the follow-up colonoscopy procedure

	Document Title	Clinical Investigational Plan For Study CL-SY-02-0096		
	Document No.	DOC001593	Revision	03

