and in another case it was initiated by the sponsor since the batteries in the capsule were already depleted and no additional benefit was expected from the procedure. In two other cases, drugs (*Picolax*) were used to expedite the expulsion of faulty capsules (that stopped working). In all four cases the total time was less than 200 hours. In one case the capsule was not retrieved by the patient at the end of the procedure and, probably lost in the sewage system. Abdominal X-ray on the following day confirmed that the capsule was expelled with no residual in the GI tract images. All cases were completed uneventfully.

Several adverse events were reported including one case of irritating sensation in the esophagus that lingered for hours after capsule ingestion, skin irritation (under the stickers), soft stool, abdominal pain, headache, radiation level (body dose) was significantly higher than the typical dose of 50 uSV and four cases in which the transit time was longer than 120 hours. Three SAE events occurred including one hemorrhage/hematoma seen on abdominal wall, one post-colonoscopy bleeding and one post-colonoscopy abdominal pain. All SAE were non-related to device or C-Scan procedure and resolved without medical intervention. Several technical malfunctions occurred during the study, none of which resulted in harm to the subject but did not provide any data regarding the performance of the C-Scan system. During the study, updates were made to the system software to continue to optimize the algorithm and the ability to collect additional physiological data.

This study demonstrated that the C-Scan procedure was safe as no device- related serious adverse event occurred in any C-Scan clinical trial and the procedure was well-tolerated by the participating volunteers. The primary end point of safety for the C-Scan system was demonstrated. The primary end point for performance in terms of Positive Percent Agreement resulted in 44% capsule vs 37% for FIT. The protocol target was set at 55%, hence superiority was demonstrated with a lower than expected result. The result of Negative Percent Agreement was 89% vs. a set target of 75%, hence target surpassed the expected result.

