### 10.3 Primary Safety Outcome Measure

The safety of the Check-Cap System will be evaluated by the incidence of device or procedure related Serious Adverse Events (SAE), as adjudicated by the Independent Physician Adjudicator.

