#### 15.1.3 Capsule Retention

There is a low risk of capsule retention, *i.e.*, no excretion of the capsule after more than 300 hours (defined as SAE). Delayed capsule excretion is defined as no excretion of the capsule after 100 hours (approximately 4 days). In some instances, intervention is required to remove the capsule. Intervention, based on the physician's decision and imaging of the capsules location may include: use of laxatives, non-soluble fiber supplements, removal by colonoscopy or surgery.

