##### 15.1.3.1 Possible Scenarios and Recommended Physician's Action:

In all cases the physician may opt to use local protocols for patients administered with gastrointestinal capsules; medical intervention or lack of, which remains at physician's discretion.

- **Capsule is Not Found After C-Scan® Track indicates it was expelled**
  - Advise the subject to look in the toilet. If it is found, the subject should notify the clinic which will arrange for the collection of the C-Scan system.
  - If the capsule is not found, the subject should speak with a physician at the clinic as there is a chance it was not expelled despite the positive indication. The physician might recommend using a laxative at home to try to expel the capsule. Make sure that the subject knows to use the collection kit during any bowel movements. Or, the physician investigator may recommend the subject to come to the clinic for a physical exam, and depending on findings, consider abdominal X-Ray imaging.
- **Capsule Not Expelled After 4 Days (~100 hours)**
  - If 4 days have passed and the capsule was not expelled, the subject should speak with a physician at the clinic (if needed, be sure to initiate a contact with the patient). The physician might recommend using a laxative at home to try to expel the capsule. Make sure that the subject knows to use the collection kit during any bowel movements. Or, the physician investigator may recommend the subject to come to the clinic for a physical exam, and depending on

	Document Title	Clinical Investigational Plan For Study CL-SY-02-0096		
	Document No.	DOC001593	Revision	03

findings, consider abdominal X-Ray imaging.

- Intervention, based on the physician's decision and imaging of the capsule's location, may include: use of laxatives, fibers, removal by colonoscopy, or by surgery.
- In case that the capsule is retained in the small bowel, as suspected according to the X-Ray imaging, the recommended Intervention, based on the physician's decision, may include: use of laxatives, prokinetic drugs, removal by SB enteroscopy (with double balloon if available) or by surgery.

- **Capsule lost communication (no flashing lights on Track) at any time between ingestion and 100 hours:**
  - Advise the subject to verify that the batteries in the Track are in position and the compartment is well secured
  - Verify that the patient is still wearing the Track on his/her back

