  - If communication is still interrupted or missing, contact the technical support to consult about potential malfunctions and interventions.
  - If the problem is not resolved and the communication is missing - have the patient come to the clinic
  - There is no reason to assume there is a safety malfunction, but since the procedure is not yielding any additional valuable clinical data, it is recommended to take steps to expel the capsule out.
  - The clinic team (technician and/or physician) should perform, in case the capsule has not been excreted and collected already, abdominal X-Ray to assure the capsule location within the GI tract.
  - Intervention, based on the physician's decision and imaging of the capsule's location, may include: use of laxatives, fibers, removal by colonoscopy, or by surgery.
- **Technical Malfunction – C-Scan® Track Sent a Fault Indication**
  - Verify that the auditory indication was from the C-Scan® Track and not a background noise. A C-Scan® Track safety fault indication is identified by a series of repeated beeps.
  - Ask the subject if a single indication was received, or was it repeated at regular intervals.
  - Ask if the subject feels any discomfort.
  - If it is a Safety malfunction (risk of higher than usual body radiation exposure), have the subject come to the clinic ASAP and no later than 48 hours post call.
  - If the capsule has not already been excreted and collected, the clinic team (technician and/or physician) should perform abdominal X-Ray to assure the capsule location within the GI tract.
  - In the case of Safety Malfunction, intervention is required to remove the capsule without delay (recommended within 24 hours). Intervention, based on the physician's decision and imaging of the capsule's location, may include: use of laxatives, fiber supplements, removal by colonoscopy, or by surgery.

	Document Title	Clinical Investigational Plan For Study CL-SY-02-0096		
	Document No.	DOC001593	Revision	03

- Efforts should be made to minimize the subject's exposure by removing the capsule out of the body.

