## 16 ADVERSE EVENTS

Subjects will be carefully monitored for adverse events. Subjects will be guided to report if they feel any pain or discomfort during the trial. At each visit or phone contact, subjects will be asked if they experienced any adverse reaction since the last visit.

Any adverse events with an onset following beginning of bowel preparation to colonoscopy procedure will not be collected. Colonoscopy related adverse events are not part of the study, are considered standard of care and will not be reported.

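### Section 16 excludes colonoscopy-related adverse events with no exception for a colonoscopy that retrieves the capsule, in conflict with sections 16.3 and 16.4.2, so a serious retrieval event could be left out of the primary outcome

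*Combined protocol and SAP*

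**What the plan says.** The second paragraph of section 16 contains two exclusions. The first works by time of onset: "Any adverse events with an onset following beginning of bowel preparation to colonoscopy procedure will not be collected". The second works by cause: "Colonoscopy related adverse events are not part of the study, are considered standard of care and will not be reported". Neither distinguishes why the colonoscopy is done.

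Elsewhere the protocol treats colonoscopy as one way to get the capsule out. Section 15.1.3 lists, for a capsule that has not passed, "use of laxatives, non-soluble fiber supplements, removal by colonoscopy or surgery". Section 15.1.3.1 says the intervention "may include: use of laxatives, fibers, removal by colonoscopy, or by surgery" both for a capsule not expelled after about 100 hours and for lost communication. For a safety malfunction it says the intervention "may include: use of laxatives, fiber supplements, removal by colonoscopy, or by surgery".

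The only primary outcome, in section 10.3, is the "incidence of device or procedure related Serious Adverse Events (SAE"), as judged by an independent physician adjudicator.

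Three other sections bear on what is collected:

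- Section 16.3 has all adverse events recorded, and both anticipated and unanticipated ones collected and reported.
- Section 16.4.1 has subjects asked about events at every visit and call. It exempts only Visit 2, described as the standard-of-care colonoscopy, and its preparation.
- Section 16.4.2 has SAEs reported within 24 hours of the investigator's awareness, with no exception.

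In the schedule of assessments (section 5 and Table 1 in section 13.1), the adverse event row is marked for Visit 1, Follow-up 1 and Follow-up 2, but not for Follow-up 3, the call after colonoscopy.

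**The concern.** The stated ground for the exclusion by cause is that colonoscopy is standard of care. That fits the colonoscopy the subject was already due to have. It does not fit a colonoscopy done, brought forward or used to take out a study capsule, because that procedure is a consequence of the device. A bleed, perforation or sedation event there is a candidate for the primary outcome. If the site follows section 16, the event is not reported, and the adjudicator cannot judge an event that was never sent.

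The two exclusions also have to be read together. An event at a prepared colonoscopy begins after bowel preparation, so the onset sentence already catches it. The cause sentence is a second barrier, and relaxing one alone would leave the other in force.

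At stake is the only primary outcome, in a study of at most 45 subjects, where one event more or less changes the reported result.

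**Working it through.** The plan gives no figure to reproduce: 45 is not derived from a power calculation, and section 14 plans descriptive statistics only. The point rests on the text; the arithmetic shows scale.

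**Step 1. The rules side by side, for harm at a colonoscopy that removes the capsule**

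| Section | Effect |
|---|---|
| 16, onset sentence | Not collected once bowel preparation has begun |
| 16, cause sentence | Not reported |
| 16.3 | Collected and reported |
| 16.4.1 | Questioning is waived only for the standard-of-care colonoscopy; says nothing on whether a known event is reported |
| 16.4.2 | If serious, reported within 24 hours |
| Schedule | No adverse event mark at Follow-up 3 |

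A site cannot tell which rule governs. Section 16.4.1 suggests a narrower intent than section 16, but it does not lift the reporting bar. A narrow reading also leaves a gap, because the scheduled colonoscopy can itself be the retrieval. Section 8.1 reports of the earlier study: "There was one case in which the capsule was retained for 100-200 hours and then removed during the follow-up colonoscopy procedure".

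**Step 2. Where the gap lies in time.** Section 15.1.3 defines non-excretion beyond 300 hours as an SAE, so that event can still count. Delay, from 100 hours, is not defined as an SAE. Harm from a colonoscopic retrieval before 300 hours therefore has no such backstop. Section 8.1 puts all four earlier intervention cases below 200 hours.

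**Step 3. How often might a retrieval occur?** The inputs are earlier counts.

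- Section 8: one capsule retrieved by colonoscopy, among more than 220 volunteers who ingested one.
- Section 8.1: one removal at the follow-up colonoscopy, among 63 subjects who ingested the capsule.
- Section 8.1, possible second case: "in another case it was initiated by the sponsor since the batteries in the capsule were already depleted". That this was a colonoscopy is inferred from the sentence and not stated.

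With retrieval rate p and 45 ingestions, the expected number is 45p and P(at least one) = 1 − (1 − p)^45.

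| p | Expected retrievals | P(at least one) |
|---|---|---|
| 1/220 | 45/220 = 0.20 | 1 − (219/220)^45 = 18.5% |
| 1/63 | 45/63 = 0.71 | 1 − (62/63)^45 = 51.3% |
| 2/63 | 90/63 = 1.43 | 1 − (61/63)^45 = 76.6% |

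These are chances of a retrieval. The documents give no rate of serious events at retrieval, so the chance of a related SAE cannot be computed; it is smaller.

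**Step 4. Effect on the primary result if one related SAE occurs and is omitted** (exact Clopper-Pearson 95% limits)

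- Counted: 1/45 = 2.2%, interval 0.06% to 11.8%.
- Omitted: 0/45 = 0%, upper limit 1 − 0.025^(1/45) = 7.9%.

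**The case against.** The strongest reply is that section 16 was meant only for the scheduled colonoscopy. Its reason, standard of care, does not describe a capsule retrieval. Section 16.4.1 uses the narrower words, and sections 16.3 and 16.4.2 require reporting without exception. Read this way, the apparent oddity that surgical or enteroscopic removal is not excluded also disappears. This carries weight. A reader might infer that section 16 plainly bars every retrieval event from the primary outcome; the documents do not support that, because they conflict. Nor does the conflict resolve itself in favour of reporting: section 16 is the specific rule, it is unqualified, and the schedule has no adverse event mark after colonoscopy.

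The earlier experience is also thin. Section 8 says the colonoscopy in the one retrieval it reports was moved earlier at the participant's request. The two faulty capsules in section 8.1 were expelled with a drug. Section 8.1 describes all these cases as uneventful. A reader might connect the two post-colonoscopy SAEs of that study with a retrieval, but it classes them as unrelated and nothing ties them to one. They show only that such events can be reported and then classified.

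A reader might also take 51% to 77% as the risk of a hidden SAE. It is not: it concerns retrievals, and the wider base of 1 in 220 gives about 18%.

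Finally, retention beyond 300 hours is an SAE, and section 16.2 has delayed excretion reported as an adverse event. Both stand as partial backstops, but neither captures harm done by the retrieval itself.

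**Conclusion.** The concern holds as a conflict in the text that can bias the primary outcome toward zero. Followed literally, section 16 could keep a serious event from a colonoscopic retrieval before 300 hours out of the count; followed through sections 16.3 and 16.4.2, the same event would be reported. The result should not depend on which section a site reads.

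The chance of at least one colonoscopic retrieval is about 18%, 51% or 77%, according to the base used. This assumes that earlier rates carry over to this study, that 45 subjects ingest the capsule and, for the last figure, that the second removal was by colonoscopy. The change from 1/45 to 0/45 further assumes that an SAE occurs, would be adjudicated as related, and is omitted, and that all 45 subjects are in the primary analysis set. No such retrieval harm is documented so far. The point merits correction because it touches the sole primary outcome and costs little to settle.

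**What to change.** Limit both exclusions in section 16, by onset and by cause, to the scheduled standard-of-care colonoscopy when it does not serve to retrieve the capsule. Add that adverse events of any procedure done, brought forward or used to retrieve the capsule, including its preparation and sedation, are collected, sent to the Independent Physician Adjudicator and eligible for the primary outcome. Then reconcile sections 16, 16.3, 16.4.1 and 16.4.2, and provide in the adverse event row at Follow-up 3 (section 5 and Table 1) for subjects whose scheduled colonoscopy was also the retrieval.

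This changes event collection only; how and when a capsule is removed stays as the protocol has it. The cost is a few sentences, a few more adverse event forms, and possibly a slightly less favourable SAE rate.

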### 16.1 Adverse Event Definitions

#### 16.1.1 Adverse Event

An Adverse Event is any unwanted medical occurrence in a subject (e.g. sign, symptom, illness, abnormal laboratory value, or other medical event) occurring to a subject that appears or worsens during a clinical study, whether or not considered related to the device.

#### 16.1.2 Serious Adverse Event

An SAE is any adverse event that:

- Led to death
- Led to a serious deterioration in the health of the subject
- Resulted in permanent impairment of a body structure or body function. Required in subject hospitalization or prolongation of existing hospitalization
- Resulted in medical or surgical intervention to prevent life threatening illness or permanent impairment to body structure or body function
- Led to fetal distress, fetal death, or congenital anomaly/birth defect

#### 16.1.3 Unanticipated Adverse Device Effect (UADE)

An unanticipated adverse event is any serious, device related adverse event, if that event was not previously identified in the risk analysis and consent form in

- Nature
- Severity or frequency
- Unreasonable risk is not defined. It shall be determined by the management on a case-by-case basis through evaluation of serious and unanticipated adverse events

#### 16.1.4 Device Malfunction/Failure

Malfunction means the failure for device to meet its performance specifications or otherwise perform as intended. In general, this is related to a component of the system not functioning as intended to provide the required outputs. Examples of a device malfunction include:

- C-Scan capsule does not traverse through the colon – the scanning of the colon is aborted prior to reaching the rectum or the image scan density throughout the colon is inadequate for clinical interpretation
- C-Scan shield does not retract – temporarily excessive radiation from the capsule
- C-Scan does not record tracking through colon- temporarily or continuous loss of tracking of the capsule by the recorder, causing inadequate or partial activation of the scanning function
- Corrupted data – the stored data in the recorder is corrupted and cannot be interpreted by the C=Scan View for clinical data analysis
- External interference – External electromagnetic interference (Hybrid cars, generators or other sources) cause interference to the communication with the capsule or to the tracking circuitry, thus causing periods of lost data during the procedure

	Document Title	Clinical Investigational Plan For Study CL-SY-02-0096		
	Document No.	DOC001593	Revision	03

- Physiological causes – subjects who fail to ingest the capsule, or subjects in which the capsule dwells in the caecum for a period of ~100 h or more, thus exceeding the operation time of the C-Scan system

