## 16.2 Anticipated Adverse Events

The following events are known potential adverse events from the C-Scan procedure. They will be reported as adverse events for the purposes of the study:

- Delayed C-Scan Capsule excretion
- Capsule retention
- Change in bowel habits
- A small amount of fresh blood in the stool
- Potential difficulty swallowing the capsule
- Abdominal discomfort during the passage of the capsule
- Abdominal pain, cramps
- Back pain
- Nausea
- Loss of appetite
- Soft/runny stool
- More than 2/day bowel movements
- Diarrhea
- Constipation
- Allergic reaction to the ingested contrast material
- Skin irritation caused by the stickers on back
- Impaired night sleep caused by the C-Scan track (recorder on the back)
- Excessive radiation exposure (> 200 [ uSv] microSivert) Note: This threshold was calculated as 2X the max body dose in a long, but normal, procedure: total transit time of 100 hours and with 4000 scanning pages, which is the maximum ever reached during a normal procedure.

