## 16.3 Recording and Documentation of Adverse Events

All adverse events should be evaluated by the Investigator, and should be medically handled per investigator discretion. All adverse events shall be recorded in the subject's Adverse Event Case Report Form. The following data should be carefully documented:

- Subject's study ID/code
- Type of event
- Time of occurrence (i.e. date & time)
- Time of resolution (i.e. date & time)
- Severity degree (mild/moderate/severe/unknown)
- Relationship to study device (definitely/probably/possibly/probably-not/not-related)
- Measures taken (e.g. concomitant medication, hospitalization, etc.)
- Event outcome (unchanged/worsened/improved/resolved/unknown/death)

Adverse events will be assessed in terms of seriousness, duration, intensity and relationship to the study device and/or procedure. All anticipated and unanticipated adverse events will be collected and reported.

	Document Title	Clinical Investigational Plan For Study CL-SY-02-0096		
	Document No.	DOC001593	Revision	03

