### **16.4.2 Serious Adverse Events Reporting**

Serious adverse events shall be reported to Check-Cap/Clinical Research Organization (CRO) in writing (using the Serious Adverse Events Form taken from the CRF) within 24 hours of the investigator's awareness of the event, and should be reported to the local Ethical Committee per their requirements.

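### Device malfunctions, including radiation shield faults, have no recording or reporting route of their own, and those captured as adverse events can still be discarded from the safety analysis

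*Combined protocol and SAP*

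**What the plan says.** The protocol's statistical plan is its section 14. These parts bear on the point:

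- **Definition (16.1.4).** One listed malfunction is a shield that fails to retract, described as "temporarily excessive radiation from the capsule".
- **Response (15.1.3.1).** A Track fault that may raise body radiation above its usual level is called a safety malfunction, and "In the case of Safety Malfunction, intervention is required to remove the capsule without delay". The means named run from laxatives to surgery.
- **Recording (16.3).** "All adverse events shall be recorded in the subject's Adverse Event Case Report Form". Malfunctions are not mentioned.
- **Reporting (16.4).** There are subsections for AEs, SAEs and UADEs only. For SAEs, "Serious adverse events shall be reported to Check-Cap/Clinical Research Organization (CRO) in writing", within 24 hours of the investigator becoming aware.
- **Dose-based AE (16.2).** The anticipated events, all to be reported as AEs, include "Excessive radiation exposure (> 200 [ uSv] microSivert"). No symptom is needed. A note says the threshold is twice the largest dose in a long but normal procedure.
- **Primary outcome (10.3).** Incidence of device- or procedure-related SAEs, as adjudicated.
- **Analysis (14.1.2, 14.1.3).** The primary safety set is the subjects whose C-Scan procedure was done per protocol. Cases where the system did not work as expected, including capsule operational failure, are removed from the trial's statistical analysis.

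**The concern.** Safety is the only primary objective, and unintended radiation is a hazard specific to this capsule. The protocol defines the fault and sets out a response to it, but never says that the fault must be written down or passed on. The analysis section then removes the cases in which the device failed.

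Two things are at stake. The first is bias: a study that discards device failures from its safety analysis can look cleaner than the device is. The second is timeliness. Section 19 lets a site hold several units at once, so a fault shared by those units need not be notified before the next subject ingests one.

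**Working it through.** **Step 1. Apply the definitions to one case.** Take a shield fault in a subject who feels well, with the capsule expelled after a laxative.

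| Category | What it requires | Is the fault captured? |
|---|---|---|
| AE (16.1.1) | an unwanted medical occurrence | not clearly, for a device fault alone |
| Anticipated AE (16.2) | dose above 200 uSv, or another listed event such as soft stool or diarrhea | only if one of these occurs |
| SAE (16.1.2) | an AE with a serious consequence | not in this case |
| UADE (16.1.3) | a serious device-related event not previously identified | no, not serious |
| Malfunction (16.1.4) | failure to perform as intended | yes, but no duty follows |

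The document list in 13.2 has no malfunction form. The call procedure in 13.6.4 attaches notification of the site study team to adverse events. A technical complaint may instead bring in the technical team.

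**Step 2. Split by dose.**
- At or below 200 uSv with no listed AE: no recording or reporting route is stated. Prompt removal limits dose, so following 15.1.3.1 makes this branch more likely.
- Above 200 uSv: the fault is an AE under 16.2 and goes on the AE form under 16.3. Under 14.1.2 and 14.1.3 the subject can still be left out of the analysis.

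Neither the schedule of assessments nor 13.2 names a step that yields a dose for each subject, so the protocol does not say how the branch is decided.

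**Step 3. Check the 200 uSv threshold against the protocol's own figures.**
- Section 16.2 states 200 uSv as twice the normal maximum: 200 / 2 = 100 uSv implied normal maximum.
- Section 7.2 gives, for the last study, mean 52, SD 38, minimum 19 and maximum 165 uSv.
- 200 / 52 = 3.8 times that mean, and (200 − 52) / 38 = 3.9 SD above it.
- 165 exceeds 100, and 2 × 165 = 330. The protocol does not say whether the 165 uSv procedure was normal, so the two passages must be reconciled.

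**Step 4. Chance of a fault in this study.** No shield-fault rate is given, so a rate p is assumed. With N = 45 (14.1.1), P(at least one) = 1 − (1 − p)^45.

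| Assumed p | P(at least one in 45) |
|---|---|
| 0.5% | 1 − 0.995^45 = 20% |
| 1% | 1 − 0.99^45 = 36% |
| 2% | 1 − 0.98^45 = 60% |

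**Step 5. Effect of discarding one case.** Suppose all 45 ingest a capsule and one has a safety malfunction.
- Kept: 1/45 = 2.2%, exact 95% interval 0.06% to 11.8%.
- Discarded: 0/44 = 0%, with upper limit 1 − 0.025^(1/44) = 8.0%.

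The intervals overlap widely. What changes is the message, from one observed event to none.

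**The case against.** A reader might infer that any shield fault without illness can vanish from every safety result. The documents do not support that. Section 16.2 makes exposure above 200 uSv a reportable AE with no symptom needed, and section 8.1 lists a raised body dose among the earlier study's adverse events. A laxative-driven expulsion may also produce a listed bowel event. Removal by colonoscopy or surgery might meet the SAE criterion on intervention to prevent permanent impairment, if the fault is first accepted as an AE. The wholly unrecorded case is therefore narrow.

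The sponsor also has informal ways to learn of a fault: at least two calls a day, technical review of the downloaded data (13.10), and return of units to the sponsor (19). The CRFs and the monitoring plan are not among the documents and may capture malfunctions. This weakens any claim that the sponsor would be unaware, but it supplies no deadline, no IRB notice and no place in the results.

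Two links are inferred. Section 15.1.3.1 does not name the shield, although both it and 16.1.4 describe raised radiation. Section 14.1.3 may have been meant for performance results only, but its wording covers the trial's statistical analysis without exempting safety.

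A reader might also take a fault rate from the two capsules in section 8.1 that stopped working and were expelled with a drug. Those are not described as radiation faults, so they say nothing about the shield.

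The gap for low-dose faults without a listed AE stands, and so does the possible loss of recorded ones from the analysis.

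**Conclusion.** The point holds in limited form. Malfunctions have a definition but no recording or reporting duty, and 14.1.2 and 14.1.3 allow device failures to leave the safety analysis even when they were recorded as AEs. Followed as written, the plan can give a falsely clean safety result.

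The size is uncertain: a 20% to 60% chance of at least one shield fault in 45 subjects rests wholly on an assumed rate of 0.5% to 2%. The conclusion also assumes that a shield fault counts both as a safety malfunction and as a capsule operational failure. The sponsor should correct this. The primary outcome definition is untouched, but the set in which it is analysed is affected.

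**What to change.** 1. In 16.3, require every device malfunction to be recorded on a CRF page, with the dose estimate, whether or not an AE occurred. State how and when that estimate is obtained.
2. In 16.4, require radiation or safety malfunctions, and removals prompted by a device fault, to be reported to the sponsor within the same 24 hours as an SAE, with notice to the IRB. Review by the Independent Physician Adjudicator is optional.
3. Amend 14.1.2 and 14.1.3 so that safety is analysed in all subjects who ingested a capsule, and device failures are not discarded from safety results.
4. Tabulate the number and percentage of those subjects with a safety malfunction, with an exact 95% interval.
5. Reconcile the 100 uSv normal maximum implied in 16.2 with the 165 uSv maximum in 7.2.

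The cost is one CRF page, one reporting sentence and one table row, plus the edits to 14.1.2 and 14.1.3 and the dose passages. The safety report may look slightly less favourable. No clinical rule needs to change.
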